## **5.9. Pharmacokinetics Analysis**

### **5.9.1. Pharmacokinetic Sampling Schedule**

Blood samples for determination of ACE-536 serum concentrations are collected at Cycle 1 Day 1, Day 1 of every 4 subsequent cycles, EOT, and EOS.

Acceptable time windows for pharmacokinetic blood draws are  $\pm$  1 day in Cycle 1 and  $\pm$  7 days for the other cycles with PK sampling scheduled.

### **5.9.2. Data Handling**

Concentrations that are below the limit of quantitation (BLQ) prior to the first dose will be assigned a numerical value of zero. Post-treatment concentrations that are BLQ will be treated as missing.

Concentrations assigned a value of missing will be omitted from the descriptive statistics. A concentration value of zero will be excluded from the computation of the geometric mean (geometric CV%). If any patients are found to be noncompliant with respect to dosing, have incomplete data, or encounter other circumstances that would affect the evaluation of pharmacokinetics, a decision will be made on a case-by-case basis as to their inclusion in the

pharmacokinetic analysis. Data excluded from pharmacokinetic analysis will be included in the data listings, but not in the summaries.

In tables and listings for the derived pharmacokinetic data, there should be four decimal places for numerical values below 1, three decimal places for numeric values below 10 but above 1, and two decimal places for numeric values above 10. However, the listings of raw data should not have more decimal places than the actual data.

### **5.9.3. Pharmacokinetic Analysis**

All ACE-536 serum concentrations will be listed by patient and scheduled time (visit and study). Actual dosing/sampling time, sample time relative to first dosing time, visit, and concentration as done for the 03 study will be presented in the listing.

The ACE-536 serum concentrations will be summarized by scheduled time, including N (number of observations), arithmetic mean, arithmetic standard deviation (SD), arithmetic coefficient of variation (CV%), geometric mean, geometric CV%, minimum, median, and maximum. Mean (SD) serum concentration-time profiles will be presented on linear scales.

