9.1. Study Design

Patients in all cohorts will receive ACE-536, administered subcutaneously (SC), every 3 weeks for up to 87 cycles or up to 1825 days, whichever occurs first. Dose titration(s), delay(s) and dose reduction(s) may be required for individual patients as outlined in the Individual Dose Modification Rules ([Section 10.8](#)).

The base study A536-03 is a phase 2, open-label, ascending dose study to evaluate the effects of ACE-536 on anemia in patients with low or intermediate-1 risk MDS who are not currently receiving treatment with an ESA. A total of up to 153 patients may be enrolled in the base study A536-03 and may be eligible for study A536-05.

Consenting patients that meet the A536-05 eligibility criteria may immediately roll over from A536-03 to study A536-05. These patients will forego the Post-treatment Follow-up (PTFU) and End of Study (EOS) visit of A536-03 to begin study A536-05. For these patients, C1D1 of A536-05 may take place 28 (\pm 7) days after the last dose administered in the base study A536-03, which may coincide with the patient's A536-03 End of Treatment (EOT) visit.

These patients will be considered "patients without treatment interruption." Patients enrolled in expansion cohorts 2 and 3 in Study A536-03 must meet the "patients without treatment interruption" criteria to be considered for the A536-05 study, unless otherwise prospectively approved by the sponsor.

Patients who complete the EOS visit for the base study A536-03 prior to C1D1 of A536-05 are considered "patients with treatment interruption." These patients will have a 28-day screening period to allow them to be re-assessed for eligibility by meeting additional inclusion criteria, as defined in [Section 9.2](#).

Patients who have completed the EOT visit for the base study A536-03 but have not reached the EOS visit (i.e. patients in the follow-up period for A536-03), may still participate, but should be treated as patients with treatment interruption and should not begin study A536-05 C1D1 until they have completed their A536-03 EOS visit so that new baseline assessments can be measured.

For patients without treatment interruption, transfusion status (NTD or TD) will carry-over from the base study A536-03. For patients with treatment interruption, transfusion status will be reassessed prior to C1D1 of study A536-05. Transfusion status for all patients is defined as follows for all patients:

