#### **Possible Starting Dose Levels with Dose Level Modifications (Reductions and Titrations)**

3 rd Dose Reduction	2 nd Dose Reduction	1 st Dose Reduction	Starting Dose Level	1 st Dose Titration	2 nd Dose Titration	3 rd Dose Titration
	0.125 mg/kg	0.25 mg/kg	0.50 mg/kg	0.75 mg/kg	1.0 mg/kg	1.33 mg/kg
0.125 mg/kg	0.25 mg/kg	0.5 mg/kg	0.75 mg/kg	1.0 mg/kg	1.33 mg/kg	1.75 mg/kg
0.25 mg/kg	0.5 mg/kg	0.75 mg/kg	1.0 mg/kg	1.33 mg/kg	1.75 mg/kg	
0.5 mg/kg	0.75 mg/kg	1.0 mg/kg	1.33 mg/kg	1.75 mg/kg		
0.75 mg/kg	1.0 mg/kg	1.33 mg/kg	1.75 mg/kg			

- Starting dose level for patients with treatment interruption is 1.0 mg/kg.
- Starting dose level for patients without treatment interruption will be last dose level administered in study A536-03 unless a dose reduction is required based upon patient dose modification rules from study A536-05.
- Patients may be titrated up and down dose levels as required per protocol to meet dose modification and titration rules.
- Patients who require more than 2 dose reductions due to an AE should be discontinued from treatment and complete the EOT, PTFU, LTFU, and EOS visits.
- The maximum dose titration will not exceed 1.75 mg/kg.

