## 4. ANALYSIS POPULATIONS

### 4.1. Intent-to-Treat (ITT) Population

The intent-to-treat (ITT) population will consist of all patients who have received at least 1 dose of ACE-536 in A536-05 study. This population will be used for all efficacy analyses.

For patients who directly rolled over from A536-03 study, both A536-03 study and A536-05 study data will be included for the analysis.

For interrupted patients, only A536-05 study data will be included for the analysis.

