 **Screening procedures:** Other than informed consent, procedures listed as part of the 28-day screening period are only applicable to patients with treatment interruption. Patients with treatment interruption will need to qualify per the additional inclusion criteria listed in Section 9.2.1. For patients without treatment interruption, C1D1 may coincide with EOT visit of the base study A536-03. Procedures that are required to confirm eligibility for patients without treatment interruption can be performed at the base study A536-03 EOT visit and used to confirm eligibility prior to dosing on C1D1 of study A536-05.

 **Study procedures** must be done prior to administration of study drug. For patients without treatment interruption, C1D1 procedures shaded grey may be conducted as part of the EOT visit for study A536-03 and may not need to be repeated for study A536-05. All screening and Cycle 1 Day 1 procedure results required to confirm eligibility must be obtained and reviewed prior to study drug administration in A536-05.

**Visit schedule:** Each dosing visit (cycles 1-87) will be 21 days ( $\pm$ 5 days) from the previous dosing visit, unless a dose delay is required. If a dose delay is required per the dose modification rules (Section 10.8), the patient will not be dosed. The patient will return every 1-3 weeks for assessment of hematology results and AEs until the patient is eligible to receive the next dose of ACE-536 and start the next cycle. The patient should resume the study at the planned dosing cycle (e.g. if the patient missed a dose at C4D1, then they would resume dosing at C4D1 and not skip to C5D1).

**Dosing:** The patient dose must be calculated based on the patient's weight on the day of dosing. Dose modification rules and titration rules must be reviewed and implemented prior to dosing as required per protocol (see Section 10.8 and Section 10.9). A dose titration cannot occur until C3D1.

 **Medical History:** Medical history for patients with treatment interruption will include medical events occurring after EOS visit in study A536-03 and prior to C1D1 for study A536-05. Medical history for patients without treatment interruption will be taken from study A536-03.

 **Quality of life questionnaires** are only required on C1D1, C5D1, C9D1, C13D1, C17D1, C25D1, C33D1, C41D1, C49D1, C57D1, C65D1, C73D1, C81D1, EOT, and EOS.

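### Serum concentrations are summarised by visit alone, so visit trends mix titration with accumulation or clearance, and the A536-05 C1D1 row may pool patients with very different residual levels

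*SAP*

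**What the plan says.** SAP 5.9.3 sets out a listing, a summary and a plot. For the summary, "The ACE-536 serum concentrations will be summarized by scheduled time", with arithmetic and geometric statistics; mean (SD) profiles are drawn on linear scales. No dose or interruption stratum is named. For the listing, scheduled time means visit and study, and actual dosing and sampling times are shown.

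On sampling, SAP 5.9.1 states: "Blood samples for determination of ACE-536 serum concentrations are collected at Cycle 1 Day 1, Day 1 of every 4 subsequent cycles, EOT, and EOS". The schedules of events require that study procedures "must be done prior to administration of study drug", so Day 1 samples are pre-dose.

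On timing, protocol 9.1 says of patients who roll over directly: "For these patients, C1D1 of A536-05 may take place 28" (±7) days after the last A536-03 dose. Interrupted patients must first complete the A536-03 EOS visit. SAP Appendix 2 places that visit 56 (±7) days after an EOT visit that is itself 28 (±7) days after the last dose.

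On dose, interrupted patients restart at 1.0 mg/kg and rollover patients continue at their last A536-03 level. Titration is assessed every cycle from C3D1 (protocol 10.9). SAP 3.1 shows starting levels from 0.50 to 1.75 mg/kg as examples, with reductions to 0.125 mg/kg, and states: "The maximum dose titration will not exceed 1.75 mg/kg".

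On values below the limit of quantitation (BLQ), SAP 5.9.2 sets those before the first dose to zero and treats those after treatment as missing. It adds: "A concentration value of zero will be excluded from the computation of the geometric mean".

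Protocol 15.1 says all populations are analysed by assigned treatment group. Protocol 15.2.4 plans Cmax, Tmax and AUC, with an optional dose-proportionality assessment. The SAP carries neither forward, and SAP 5.13 does not list either as a change.

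**The concern.** The PK profile is a secondary objective, and the by-visit table and plot are the only PK summaries that the SAP plans. A reader will naturally take a rising mean as accumulation, or a falling one as increased clearance. Under individual titration with dose-proportional exposure, the mean also moves when patients change dose.

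A second and narrower problem arises at the first A536-05 sample. Two groups at very different times since their last dose may be averaged in one row, which sets the starting point of the plotted profile. If some of those values are BLQ, the arithmetic and geometric means in that row may also describe different patients.

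**Working it through.** The documents give no PK figure to reproduce, so the checks below use their timing, dose and half-life inputs.

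**Inputs.** Half-life T = 14.9 to 16.2 days, with dose-proportional AUC and Cmax (protocol 7.3, healthy postmenopausal women at 0.0625 to 0.25 mg/kg; use in MDS is an assumption). Time since last dose at A536-05 C1D1: 28 days for rollover patients (window 21 to 35) and 28 + 56 = 84 days at the earliest nominal timing for interrupted patients (window 70 to 98). Dosing is every 21 days. Decay is taken as first-order and absorption is ignored.

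**1. Residual level at C1D1** = 2^(−t/T).
- Rollover, t = 28: 0.272 (T = 14.9) to 0.302 (T = 16.2).
- Interrupted, t = 84: 0.020 to 0.027.
- Ratio = 2^(56/T): 13.5 (T = 14.9) to 11.0 (T = 16.2). Over the visit windows it runs from about 4.5 (35 v 70 days, T = 16.2) to 36 (21 v 98 days, T = 14.9).

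Counting decay from Tmax (7.0 to 9.8 days) instead of from injection raises both residuals, but leaves the nominal ratio unchanged because the 56-day gap is the same.

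**2. Effect on a pooled C1D1 mean.** The share of interrupted patients, w, is not given. With T = 15.5 days the interrupted level is 1/12.2 = 0.082 of the rollover level, and the pooled mean relative to the rollover mean is (1 − w) + 0.082w. For assumed w of 10%, 25% and 50% this gives 0.91, 0.77 and 0.54.

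**3. Does interruption matter later?** At C5D1 an interrupted patient has had four A536-05 doses. The fraction of the steady-state pre-dose level is 1 − q^4 with q = 2^(−21/T), which is 0.973 to 0.980. A rollover patient with nine doses (five in A536-03, four in A536-05, ignoring the 28-day gap) exceeds this by (1 − q^9)/(1 − q^4) = 1.02 to 1.03 at equal dose. The interruption effect is therefore confined to C1D1.

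**4. Titration.** As an illustration, take a patient on 1.0 mg/kg for two cycles, 1.33 from C3D1 and 1.75 from C5D1, with T = 15.5 and q = 0.391.
- Pre-dose C5D1: 1.33(q + q²) + 1.0(q³ + q⁴) = 0.806.
- Pre-dose C9D1: 1.75(q + q² + q³ + q⁴) + 1.33(q⁵ + q⁶) + 1.0(q⁷ + q⁸) = 1.116.
- Ratio 1.116/0.806 = 1.38. At constant dose the ratio is 1 + q⁴ = 1.02.

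The level rises about 38% with no change in clearance.

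**5. Spread from dose mix alone** under dose proportionality (SD/mean of dose).
- Equal mix of the five listed starting levels: 0.439/1.066 = 41%.
- Assumed titrated-up mix (15% at 1.0, 15% at 1.33, 70% at 1.75): 0.283/1.5745 = 18%.
- Equal mix of all seven ladder levels: 0.544/0.815 = 67%.

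**6. Label and BLQ rule.** Some C1D1 procedures for rollover patients may be done at the A536-03 EOT visit, where PK is also sampled (SAP Appendices 2 and 3). If those samples carry the A536-05 C1D1 label, that row pools the two groups. If they carry the A536-03 EOT label, the A536-05 C1D1 row holds mainly interrupted patients and C5D1 holds both groups, so the first step of the profile is a change in who is counted. For a BLQ value in an interrupted patient at C1D1, the result depends on the meaning of first dose. If it is the first A536-05 dose, the value is zero, enters the arithmetic mean and leaves the geometric mean. If it is the first A536-03 dose, the value is missing from both. The SAP settles neither question.

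**The case against.** A reader might infer that the whole mean profile is uninterpretable. The documents do not support that. The interruption effect all but disappears by C5D1, individual concentrations are listed with actual times, and SAP 5.6 lists dosing. Dose-specific review is possible, although the PK listing does not name dose as a column and the two listings would have to be merged.

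A reader might also infer that a 14-fold dose range is being averaged (1.75/0.125 = 14). That is the outer limit of a ladder given as examples. The two lowest levels appear only as reductions, and the titration rules move patients without sufficient response upward. Nothing shows that anyone contributes samples at 0.125 mg/kg. The listed starting levels span 1.75/0.50 = 3.5-fold.

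Pooling at C1D1 is possible, not established. The sample label is unstated, and the grey shading that marks shared procedures could not be seen in the text reviewed. Expansion cohorts 2 and 3 generally had to enter without interruption, which limits the number of interrupted patients. Nor can interrupted patients be called fully washed out: about 2 to 3% may remain, and whether that is BLQ depends on an assay limit that is not given. The rule in SAP 4.1, "For interrupted patients, only A536-05 study data will be included for the analysis", governs the ITT population and does not settle the data scope for PK.

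Finally, everything here is descriptive, the primary objective is safety, and SAP 5.9.3 derives no accumulation or clearance parameter. All of this stands, and it limits the importance of the point. It does not answer the dose-mix problem, which persists at every later visit.

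**Conclusion.** The point holds as a cheap improvement. As written, changes in the pooled visit means cannot be read as accumulation or clearance, because they also reflect dose mix. One plausible titration path alone moves the pre-dose level by about 38% between C5D1 and C9D1, and dose mix alone contributes a CV of 18 to 67% depending on the mix assumed. At A536-05 C1D1 only, the two entry groups differ about 11- to 13.5-fold in residual level at nominal timing and equal prior dose, and may be pooled.

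These sizes rest on a healthy-volunteer half-life and dose proportionality carried over to MDS, first-order decay, and assumed dose mixes. The share of interrupted patients is unknown, so the effect on the C1D1 mean is a range and not an estimate.

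**What to change.** In SAP 5.9.3, summarise and plot concentrations either dose-normalised or by the dose level of the preceding dose. Show A536-05 C1D1 separately by interruption status; later visits do not need that split. State whether rollover C1D1 samples are labelled A536-03 EOT or A536-05 C1D1.

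In SAP 5.9.2, define first dose for the BLQ rule, so that the arithmetic and geometric means in a row describe the same patients.

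In SAP 5.13, reconcile the PK analysis with protocol 15.1 and 15.2.4. Either implement grouping by treatment and the non-compartmental and dose-proportionality analyses, or record that they are dropped. The protocol's assigned treatment group should be defined at the same time: grouping by starting dose alone would not remove the titration effect.

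No added restriction to pre-dose samples is needed, since pre-dose sampling on dosing days is already required.

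The cost is extra table columns and some small cells at less-used dose levels. No new data are needed.

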## **5.10. Interim Analysis**

There are no planned interim analyses. However, safety and erythroid response data may be reviewed periodically throughout the study.

## **5.11. Protocol Violations or Deviations**

Protocol violations and deviations will be reviewed and may result in a patient and/or patient visit data being excluded from the statistical summaries. All decisions regarding exclusion of any patient data will be made and recorded during the final data review.

### **5.11.1. Violation Criteria**

Patients who meet any of the following criteria will be listed:

- Non-compliance with inclusion criteria
- Non-compliance with exclusion criteria
- Unauthorized concomitant therapy
- Less than 8 weeks historical hemoglobin data
- Dose not modified according to Dose Modification Criteria
- Study assessment outside of visit window

### **5.11.2. Protocol Deviations**

Deviations from the protocol, as defined in the protocol, will be documented on an ongoing basis by the study monitors and project manager throughout the study period.

At the time of database lock and while the protocol violations are being reviewed, the project manager will forward all relevant documentation highlighting protocol deviations to the study

statistician. These deviations will be included in the protocol violation document for agreement and will be listed with the protocol violations in the CSR.

## **5.12. Handling of Missing Data and Visit Window**

### **5.12.1. Missing Data**

As a general principle, no imputation of missing data for other variables will be done. Exceptions are the start and stop dates of AEs and concomitant medication. The imputed dates will be used to allocate the medication as prior or concomitant medications and to determine whether an AE is/is not treatment emergent. Listings of the AEs and concomitant medications will present the actual partial dates; imputed dates will not be shown.

### **5.12.2. Missing Dates for Adverse Event**

Imputing partial AE start dates:

- If the year is unknown, the date will not be imputed and will be assigned a missing value.
- If the month is unknown, then:
  - If the year matches the first dose date, then impute the month and day of the first dose date.
  - Otherwise, assign January.
- If the day is unknown, then:
  - If the month and year match the first dose date, then impute the day of the first dose date.
  - Otherwise, assign '01'.

Imputing partial AE stop dates:

- If the year is unknown, the date will not be imputed and will be assigned a missing value.
- If the month is unknown, then assign December.
- If the day is unknown, then assign the last day of the month.

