### 5.8.6. Adverse Events

All AEs and SAEs occurring after the Study A536-03 (for patients without interruption) or Study A536-05 (for patients with interruption) Cycle 1 Day 1 until approximately 2 months after the last study drug administration (PTFU visit) are to be reported and documented on the AE CRF.

Treatment emergent adverse events (TEAE) are defined as:

- AE starting or worsening from the first date of study drug;
- AE occurs on the first date of study drug and the onset check box is marked “Onset after first dose of study drug”;
- AE with a missing start date and a non-missing stop date on or after the first dose of study drug;
- AE with both a missing start and stop date.

A drug-related TEAE is defined as any TEAE related to the study medication as assessed by the investigator or with missing assessment of the causal relationship.

The following summaries will also be presented:

- Number and percentage of patients reporting each AE, categorized by SOC and PT
- Number and percentage of patients reporting each AE experienced by  $\geq 5\%$  of patients in all patients by PT
- Number and percentage of patients reporting SAE, categorized by SOC and PT
- Number and percentage of patients reporting Grade  $\geq 3$  AE, categorized by SOC and PT
- Number and percentage of patients reporting related AE, categorized by SOC and PT
- Number and percentage of patients reporting AE leading to drug withdrawal, categorized by SOC and PT
- Number and percentage of patients reporting AEs of interest by cycle

Note that counting will be by patient, not event, and patients are only counted once within each SOC or preferred term. If a patient has the same AE at more than one severity, or with more

than one relationship to study drug, the most severe rating or the stronger causal relationship to study drug will be given precedence. Any missing severity, causality, or outcome will not be imputed and classed as unknown.

All AEs will be listed. The following listings will also be provided: 1) patients with SAEs; 2) patients with Grade  $\geq 3$  AEs; 3) patients with AEs leading to discontinuation.; and 4) death.

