### **5.12.3. Missing Dates for Concomitant Medication**

If start date is missing or partial:

- if month is missing, use January
- if day is missing, use the first day of the month under consideration
- if year is missing, use year of the informed consent date
- if entire date is missing, use informed consent date

If stop date is missing or partial:

- if month is missing, use December
- if day is missing, use the last day of the month under consideration
- if year or the entire date is missing, set to December 31st, 2099

If the imputed start date is after the stop date, then the imputed start date will be one day prior to the stop date.

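### The adverse-event start-date rule in SAP 5.12.2 ignores the stop date, so an event recorded as over before the first dose can be counted as treatment-emergent

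*SAP*

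**What the plan says.** SAP 5.12.2 handles partial start dates of adverse events. With the month unknown: "If the year matches the first dose date, then impute the month and day of the first dose date". With only the day unknown: "If the month and year match the first dose date, then impute the day of the first dose date". Partial stop dates go to the latest possible date, for example "If the day is unknown, then assign the last day of the month". Nothing in 5.12.2 compares the imputed start with the stop.

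SAP 5.12.1 says the imputed dates serve "to determine whether an AE is/is not treatment emergent". SAP 5.8.6 then gives four alternative criteria for a TEAE. The first is "AE starting or worsening from the first date of study drug". The second covers the first dosing day: "AE occurs on the first date of study drug and the onset check box is marked" to show onset after dosing. The third is "AE with a missing start date and a non-missing stop date on or after the first dose of study drug". The fourth takes in events with neither date.

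For concomitant medications, SAP 5.12.3 does have a stop-date check: "If the imputed start date is after the stop date, then the imputed start date will be one day prior to the stop date". SAP 5.13, which lists departures from the protocol, does not mention the matter.

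**The concern.** Dating an uncertain onset to the first dose is a sensible conservative default while on-treatment onset remains possible. It makes no sense once a recorded stop date rules that out. The SAP recognises this in two neighbouring places: for a wholly missing start in 5.8.6, and for medications in 5.12.3. Only partial starts of adverse events lack the check. As a result, a record with some onset information can be classified worse than the same record with none.

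Long-term safety and tolerability is the primary objective, and TEAE incidence is one of the safety endpoints named in SAP 5.8.5. A misdated record would enter the overall TEAE table and, according to its attributes, the serious and Grade 3 or higher tables. The listings show the recorded partial dates and not the imputed ones (SAP 5.12.1). A reader could notice a stop before the first dose but would not see the impossible onset that drove the classification.

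**Working it through.** The plan states no figure to reproduce, because this is a derivation rule. The check applies the rules in order to test records.

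**Inputs.** Start and stop imputation come from SAP 5.12.2, the use of imputed dates from 5.12.1, the TEAE criteria from 5.8.6, and the maximum of 153 patients from 3.3. The first-dose date of 15 Jun 2015 is invented for illustration. The column for the current result applies the first criterion in 5.8.6 as written.

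| | Recorded start | Recorded stop | Start used | Stop used | TEAE now | TEAE with stop-date check |
|---|---|---|---|---|---|---|
| A | 2015 only | 10 Mar 2015 | 15 Jun 2015 | 10 Mar 2015 | yes | no |
| B | Jun 2015 | 5 Jun 2015 | 15 Jun 2015 | 5 Jun 2015 | yes | no |
| C | 2015 only | Mar 2015 | 15 Jun 2015 | 31 Mar 2015 | yes | no |
| D | wholly missing | 10 Mar 2015 | missing | 10 Mar 2015 | no | no |
| E | May 2015 | 5 Jun 2015 | 1 May 2015 | 5 Jun 2015 | no | no |
| F | 2014 only | 10 Mar 2015 | 1 Jan 2014 | 10 Mar 2015 | no | no |
| G | 2015 only | Jun 2015 | 15 Jun 2015 | 30 Jun 2015 | yes | yes |

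- In record A the onset falls 21 + 30 + 31 + 15 = 97 days after the event ended.
- A and D differ only in that A has a known start year. D is left out and A is counted.
- E and F show the limit of the problem: a partial start outside the first-dose month or year is unaffected.
- G shows that a stop-date check does not remove events that could have begun on treatment.

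**Not an artefact of the dates chosen.** Pairing every first-dose date in a 365-day year with every earlier stop date in that year, start month and day unknown, gives 365 × 364 / 2 = 66,430 combinations. All 66,430 become TEAEs under the current rule. With the guard from 5.12.3 carried over, none do. This follows by logic: if stop < first dose and start ≤ stop, then start < first dose. The count shows that the rule fails every time its conditions are met. It says nothing about how often they are met in the trial.

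**Scale.** One patient is at least 1/153 = 0.65 percentage points. SAP 5.8.6 plans a table of events seen in at least 5% of patients. At N = 153 the cut lies between 7/153 = 4.6% and 8/153 = 5.2%, so one misclassified patient could move a term across it.

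**The case against.** **Few records are exposed.** This largely stands. SAP 5.8.6 directs the adverse-event CRF to events after Cycle 1 Day 1. Protocol 12.2 and 14.5 send non-serious pre-dose events of interrupted patients to medical history, and Protocol 14.5.1 limits serious events on that CRF to those after the first dose. Two narrow routes remain. The A536-03 schedule (SAP Appendix 2) marks Screening in a row that combines concomitant medications and adverse events, and SAP 4.1 includes A536-03 data for roll-over patients. That mark does not prove that screening events reach the adverse-event dataset. Malignant and premalignant events are reported from consent (Protocol 11.3), but would also need a partial start and a stop before dosing.

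**The check box may govern the first dosing day.** On that reading, an unmarked record imputed to that day is not a TEAE, and A to C come out right. The first criterion as written includes that day without reference to the box, so the two criteria overlap and the SAP should say which applies. The check-box reading also has a cost: an ongoing event imputed to the first-dose date would drop out unless the box was marked, which defeats the purpose of the default.

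**Medications need a guard more than events do**, since they are collected before dosing by design. That is fair, but the third criterion in 5.8.6 already consults the stop date for adverse events.

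**Stronger readings.** A reader might infer that the primary safety results are materially inflated. The documents do not support that: they give no count of such records, and the study is single-arm and descriptive with no hypothesis tests, so no comparison is biased. A reader might also infer that the table of related events is contaminated. Protocol 14.4 requires a plausible time sequence after dosing for a possible or probable rating, so an event resolved before dosing should rarely be rated related. Nor is it settled that every pre-dose event on Day 1 counts, since that too turns on which criterion governs.

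**Conclusion.** The point holds as a certain gap in a stated rule with a probably very small effect. For a partial start in the first-dose year (month unknown), or in the first-dose month and year (day unknown), a recorded stop before the first dose is ignored and the event becomes a TEAE. Complete starts, wholly missing starts and partial starts in other periods are unaffected. The direction is always an overcount.

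The conclusion rests on three assumptions. The first criterion in 5.8.6 is applied as written. Some pre-dose records with partial starts reach the adverse-event data; their number is not in the documents. For roll-over patients, the first-dose date means the first dose in A536-03; SAP 4.1 and 5.8.6 imply this, but 5.12.2 does not say so.

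**What to change.** In SAP 5.12.2, impute a partial start to the first-dose date only if the stop date, after imputation where partial, is missing, ongoing, or on or after the first-dose date. Otherwise the imputed start may not be later than the stop date, and the event is not treatment-emergent. The section's existing defaults of January and the first of the month would meet this whenever the recorded start and stop are consistent.

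In SAP 5.8.6, state two things. For an event with a complete recorded start on the first-dose date, the check box in the second criterion governs. An event whose start is imputed to the first-dose date stays treatment-emergent, including when it is ongoing or its stop date is missing.

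The second statement is needed. Merely changing the first criterion to starts strictly after the first-dose date would drop ongoing events imputed to that date whenever the box is unmarked, replacing a conservative overcount with an undercount.

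The cost is a few sentences of SAP text and a small programming change before database lock. The downside is that a few events leave the TEAE tables; they stay in the listing of all adverse events.
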